Study design: multicenter, randomized, double-blind, placebo-controlled, parallel-group, dose-ranging study of 12-week treatment with 3 doses of luseogliflozin or placebo on top of metformin

The study will consist of 3 periods: selection period up to 2 weeks, double-blind treatment period with 4 parallel groups (doses 2.5 mg, 5 mg, 10 mg of luseogliflozin and placebo) on top of metformin for 12 weeks and the follow up period for 2 weeks after double blind treatment stop.

Number of participants:

Planned: 320 patients included into the study and randomised using Interactive Response System (IRS) with a randomization ratio 1:1:1:1 (80 patients in 2,5 mg Luseogliflozin group; 80 patients in 5mg Luseogliflozin group; 80 patients in 10 mg Luseogliflozin group; 80 patients in placebo group)

Diagnosis and main criteria for selection:

Out-patients (male and female) of Caucasian race aged 18-75 years inclusive with type 2 diabetes mellitus (diagnosed for not less than 3 months prior to selection), treated with metformin in stable dose equal or more than 1500 mg daily for at least 3 months and with inadequate glycemic control (HbA1c 7.5 %-10.0 % at

Name of the sponsor: JSC Servier	Individual Study Table Referring to Part of the Dossier	(For National Authority Use only)
Name of Finished Product:	Volume:	
Name of Active Ingredient: Luseogliflozin	Page:	

central laboratory).

Body mass index less than 36 kg/m2,

Absence of any severe, uncontrolled conditions incompatible with study treatment or likely to interfere with the conduct of the study.

Test drug:

Name: Luseogliflozin

Dosage form: film-coated tablet

Dosages: 2,5 mg; 5 mg of luseogliflozin

Comparator:

Placebo

Dosage form: film-coated tablet

Dose regime:

Patients will have to take 3 tablets once daily orally before breakfast starting next day after inclusion visit and ending at Week 12 visit.

IMP intake will be as follows:

2.5 mg group: one tablet of Luseogliflozin 2.5 mg, one tablet of Placebo 2.5 mg and one tablet of Placebo 5 mg

5 mg group: two tablets of Luseogliflozin 2.5 mg and one tablet of Placebo 5 mg

10 mg group: two tablets of Luseogliflozin 2.5 mg and one tablet of Luseogliflozin 5 mg

Placebo group: two tablets of Placebo 2.5 mg and one tablet of Placebo 5 mg

Duration of treatment:

Selection period: no study treatment during 1-2 weeks

Double blind treatment period:12 weeks

Follow up period: no study treatment 2 weeks after double-blind treatment stop

Criteria for evaluation:

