7.2. Methods and measurement times

The study visits should be performed in the morning in fasting conditions before IMP intake on the day of the visit. IMP intake on the day of the Week 4 and W8 visits should be done from a new pack allocated using IRS at the visit.

HbAlc at central laboratory will be measured at selection, inclusion, W 8 and Week 12 visit. Fasting plasma glucose, body weight and waist circumference are to be measured at each study visit. Waist circumference will be measured at midway between the lowest ribs and the iliac crest in the standing position at the end of normal expiration, the tape should be in horizontal plane.

Before the start of the treatment (W0) and the end of the double-blind treatment (W12) blood will be collected 2 hours after the start of the standardized meal, and plasma glucose will be measured. A standardized meal (breakfast) containing energy about 600 kcal will provided. At W12 visit the IMP should be taken during the visit before standardized breakfast.

Regarding the PK assessment, in the subset of patients the sampling should be performed at Week 4 visit; 12 samples per patients are planned. Sampling times are as follows: T0 (before administration); 0.25 (15 min); 0.5 (30 min); 1; 1.5; 2; 3; 4; 6; 8; 12 and 24 hours after administration. In this subset of patients the 24-hour urinary glucose excretion will be measured at Week 0 and Week 4 visits as well. The diet, fluid intake and physical activity during the days of 24-hour urine collection at W0 and W4 should be similar as far as possible. The detailed instructions regarding the food, fluid, physical activity etc. related to 24-hour urine collection and the conditions for blood sampling will be described in the Investigator's Guide for PK/PD.

At visits, the proper timing of both drug intake and of blood sampling should be collected.

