9.2. Measurement of drug concentration

Measurement of plasma concentration of luseogliflozin will be performed in a subset of patients in each dose group of luseogliflozin. Eighteen patients per group are planned to be included at sites, participating in PK/PD assessment and who signed a specific informed consent form.

The patients from the PK/PD subset will be hospitalized for at least 24 hours (depending on the center organization) at the visit Week 4. The first blood sample for evaluation of the pharmacokinetic parameters will be collected in the morning before administration of IMP at

Week 4. Serial blood sampling up to 24 hours will follow IMP administration; totally, 12 samples per patient will be collected. Sampling times: T0 (before administration); 0.25; 0.5; 1; 1.5; 2; 3; 4; 6; 8; 12 and 24h after administration. Around 6 mL venous total blood for each sample will be collected into lithium-heparinised tubes.

The actual time of IMP intake and blood sampling will be recorded on the sample requisition form sent to the pharmacokinetic laboratory.

Pharmacokinetic analysis will be performed by the Exacte Labs (Russia).

Sampling, handling and shipment procedures will be detailed in the laboratory manual provided by the pharmacokinetic laboratory. This investigator manual will be sent to the investigator prior the start of the study and explained in detail during the initial monitoring visit. The investigator will be responsible for strict compliance to the instructions.

Plasma levels of luseogliflozin will be determined by a validated HPLC-MS/MS assay (high performance liquid chromatography, tandem mass spectrometry). The lower limit of quantification (LLOQ) of luseogliflozin will be no more than 0.1 ng/ml. The upper limit of quantification (ULQ, ULOQ) luseogliflozin will depend on the linearity of the LC-MS/MS method. Dilution integrity will be validated if necessary to cover the concentration range in the study samples. Evaluation of dilution integrity may be covered by partial validation.

Validation of HPLC-MS/MS method includes the following parameters:

- selectivity;
- linearity;
- lower limit of quantification (LLOQ);
- calibration range;
- inter-run/batch and intra-run/batch precision and accuracy;
- carry-over;
- recovery;
- matrix effect;
- stability.

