9.3. Pharmacokinetic assessment

Pharmacokinetic analysis will be performed by the Exacte Labs (Russia) under responsibility of the Division of Clinical Pharmacokinetics and Pharmacometrics in Servier.

The datasets needed for final analyses will be prepared by extraction under the responsibility of the clinical Business Intelligence Department using SAS® program and following the clinical PK project manager specifications.

NCA report will be subcontracted and the report will be writing by the responsible person of the Contract Research Organisation (CRO) using I.R.I.S. (Institut de Recherche Internationales Servier) format, under the responsibility of the PK actor.

The non-compartmental pharmacokinetic analysis (NCA) will be performed under the supervision of the Division of Clinical Pharmacokinetics using PhoenixWinNonlin® or Excel on the individual concentration-time data of luseogliflozin after the administration of study treatment, using the exact administration and sampling times for final analysis. Descriptive statistics, tables and figures will be generated using PhoenixWinNonlin® and Excel®.

Any suspicious concentration will be investigated and kept in the PK analysis if possible. All excluded concentrations will be justified in the report.

To calculate PK parameters, BLQ concentrations before the first concentration measured above the limit of quantification (e.g. before administration and in the ascending part of the plasma concentration-time curve) will be substituted by zero whereas other BLQ values will be left as BLQ and ignored in the NCA. When a single BLQ value occurred between two adjacent quantifiable values, it will be excluded from the analysis. However, when concentrations are BLQ for the whole profile of a participant, they will be substituted by zero and included in the analysis. A missing concentration will be stated MS (Missing) and ignored in the NCA.

The pharmacokinetic analysis will be performed on the pharmacokinetic set (PKS). The PKS corresponds to all included participants having completed treatment period without deviation affecting pharmacokinetic interpretation.

Summary statistics (n, mean, SD, min, median, max, Coefficient of Variation (CV)) will be calculated for these PK parameters as well as on concentrations-time profiles using PhoenixWinNonlin® and Excel®.

The pharmacokinetic parameters (Table 4) will be calculated from the measured plasma analyte concentrations using a noncompartmental method.

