- Frequency of adverse events related to the conditions of the protocol;
- Frequency of any adverse events leading to treatment withdrawal;
- Frequency of all AE of Special Interest and frequency of each individual AEOSI;
- Laboratory parameters by visit;
- Frequency of laboratory parameter abnormalities by visit;
- Vital signs (HR, SBP, DBP) by visit;
- Frequency of vital signs (HR, SBP, DBP) abnormalities by visit;
- 12-lead ECG results by visit;
- Frequency of 12-lead ECG abnormalities by visit.

Frequency data will be compared between the groups using exact Fisher tests; numeric data will be compared between the groups using the t-test or Wilcoxon-Mann-Whitney test on ranks depending on the normality of the parameter distribution (which will be tested using Shapiro-Wilk test). Laboratory parameters, vital signs and 12-lead ECG data will be analysed using two-way ANOVA (or ANOVA on ranks, if the distribution is not meeting the normality criteria) to account for group and visit factors simultaneously.

Interim analysis

No interim analysis is planned for this study.

Study populations

- Randomized Set (RS):

All patients to whom a therapeutic unit was randomly assigned using IRS.

- Per Protocol Set (PPS):

All the patients of the RS that do not have any significant protocol deviations. List of deviations will be reviewed for the determination of their significance prior to the database lock and randomization list unblinding.

- Safety Set (SS):

All patients having taken at least one dose of study drug.

- **Pharmacokinetic set**: all patients for whom blood samples were collected with no deviations that might affect the pharmacokinetic interpretation

- **Pharmacokinetic/Pharmacodynamic set:** all included patients for whom blood samples and 24-hour urinary glucose measurements were collected with no deviations that might affect the PK and/or PD interpretations.

Significance level:

The type I error of the statistical tests will be set at 5% (two-sided situation).

Multiplicity issues:

In order to take into account the multiplicity of comparisons associated with the primary objective of the study (demonstration of superiority of at least one luseogliflozin dose as compared to placebo on the primary efficacy endpoint); a Bonferroni correction will be used for the primary analysis.

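### The pharmacokinetic set has two incompatible definitions, and the one in section 9.3 excludes valid Week 4 profiles of patients who stop treatment later

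*Protocol*

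**What the plan says.** The protocol defines the pharmacokinetic set three times.

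- Section 9.3 names the pharmacokinetic set (PKS) as the set for the PK analysis and says it consists of "all included participants having completed treatment period without deviation affecting pharmacokinetic interpretation".
- Section 10.1, under Study populations, defines it as "all patients for whom blood samples were collected with no deviations that might affect the pharmacokinetic interpretation".
- The analysis-set list in the study summary sheet uses the same wording as section 10.1.

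The separate pharmacokinetic/pharmacodynamic set in section 10.1 covers "all included patients for whom blood samples and 24-hour urinary glucose measurements were collected with no deviations" that might affect PK or PD interpretation. It has no completion condition either.

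On timing, section 7.2 says that "in the subset of patients the sampling should be performed at Week 4 visit; 12 samples per patients are planned", the last of them 24 hours after dosing. The summary sheet gives the treatment period: "Double blind treatment period:12 weeks". On size, section 9.2 says "Eighteen patients per group are planned to be included at sites, participating in PK/PD assessment".

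**The concern.** The completion condition appears only in section 9.3. A patient with a clean Week 4 profile who stops the study drug at Week 6 belongs to the set under section 10.1 and the summary sheet, but not under section 9.3. Neither section refers to the other or takes precedence. Section 9.3 also says that the non-compartmental report is subcontracted. Its authors may follow the PK section while the trial statisticians follow section 10.1, so one named set could be reported with two different patient counts.

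The condition also serves no pharmacokinetic purpose, because it selects patients on something that happens after their data are complete. If the reason for stopping is related to exposure or response, the remaining patients are not a fair sample of those who were measured. The PK summary statistics and the dose-proportionality assessment in section 9.5 would then rest on a selected group.

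**Working it through.** The plan states no figure to reproduce here. The check compares the definitions with the schedule and then sizes the loss under stated assumptions.

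**Definitions against the schedule**

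| | Section 9.3 | Section 10.1 and summary sheet |
|---|---|---|
| Completion of treatment period required | yes | no |
| Blood samples required | not stated | yes |
| No deviation affecting PK interpretation | yes | yes |
| Valid Week 4 profile, stops in Weeks 5 to 12 | out | in |

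The only treatment period the protocol defines is the 12-week double-blind period (summary sheet; section 4.2.1). Sampling happens once, at Week 4, so every parameter in Table 4 is fixed about 12 − 4 = 8 weeks before that period ends.

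**Could later stopping be informative?** Section 5.7.1 lists loss of glycaemic control, a fall in eGFR and adverse events among the reasons for withdrawal. HbA1c "will be measured at selection, inclusion, W 8 and Week 12 visit", so a scheduled on-treatment HbA1c result that leads to withdrawal comes after the PK profile. Stops of this kind concern response, while adverse-event stops concern tolerability. The two could select in opposite directions.

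**Profiles lost.** Inputs: n = 18 per dose (section 9.2), or 3 × 18 = 54 over three doses. The share d stopping between Week 4 and Week 12 is an assumption. Expected loss is n × d; the chance of losing at least one of 54 is 1 − (1 − d)^54.

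| Assumed d | Lost of 18 | Lost of 54 | Chance of at least one of 54 |
|---|---|---|---|
| 5% | 0.9 | 2.7 | 94% |
| 10% | 1.8 | 5.4 | 99.7% |
| 15% | 2.7 | 8.1 | >99.9% |

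Over a wider range of 3% to 20%, the loss per dose runs from 0.5 to 3.6 of 18.

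**Precision, if stopping is unrelated to exposure.** The standard error rises by the factor √(18/(18 − k)) when k profiles are lost: √(18/17) = 1.03, √(18/16) = 1.06 and √(18/15) = 1.10.

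**Worst case for the mean.** Assume lognormal exposures, and that exactly the highest 1, 2 or 3 of 18 leave (20,000 simulated samples). The between-patient coefficients of variation are also assumptions.

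| Highest exposures lost | CV 25% | CV 40% |
|---|---|---|
| 1 of 18 | −3.1% | −5.4% |
| 2 of 18 | −5.6% | −9.3% |
| 3 of 18 | −7.7% | −12.7% |

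**Worst case for the power-model slope.** If the same truncation hits only the 10 mg group, the slope moves by −0.02 to −0.05 (CV 25%) or −0.03 to −0.08 (CV 40%). For doses 2.5, 5 and 10 mg with 18 each, the slope's standard error is σ/√(18 × 2 × (ln 2)²) = σ/4.16, where σ = √ln(1 + CV²) is 0.246 or 0.385. This gives 0.059 or 0.093. Even this extreme shift is smaller than one standard error. With equal truncation in all three dose groups the slope hardly changes.

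**The case against.** The strongest reply is that little depends on this. PK is an exploratory objective in a subset and is reported descriptively. Section 9.3 makes fixing the PK population the first step of the analysis, and detail may be left to the SAP. The low stakes are accepted. However, the protocol has not left the matter open: it states the rule more than once, in incompatible ways.

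One could also read the treatment period in section 9.3 as dosing up to the PK day. That would remove the conflict, but the protocol defines no such period.

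Several stronger readings are tempting and are not supported:

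- **Exposure is biased downwards, chiefly at 10 mg.** Nothing in the protocol ties stopping to high exposure or to the top dose. Section 2 describes the drug as well tolerated. Withdrawal for loss of glycaemic control could equally remove patients with low exposure, which would push the mean up.
- **Any PK/PD model is affected.** PK/PD has its own set with no completion condition, and section 9.5 puts population PK and PK/PD modelling in a separate plan.
- **The dose-proportionality slope would be materially distorted.** Even the extreme case moves it by less than one standard error.
- **Section 9.3 overrides section 10.1.** The protocol does not rank them.

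**Conclusion.** The two definitions conflict. Following section 9.3 as written discards valid Week 4 profiles because of later events that cannot alter them. This much rests on the text alone.

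The size rests on assumptions, since the protocol gives no dropout rate. With 5% to 15% stopping between Weeks 4 and 12, about 0.9 to 2.7 of 18 profiles per dose are lost, and the standard error rises about 3% to 10% for 1 to 3 lost. A reader might take the 3% to 13% fall in mean exposure as the expected effect. It is only the worst case, in which precisely the highest exposures leave, and the direction of any real bias is unknown.

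The consequence stays within the exploratory non-compartmental and dose-proportionality results. The primary, secondary and safety conclusions do not depend on this set. It is a correction worth making, with low stakes.

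**What to change.** Use one definition in the summary sheet, section 9.3 and section 10.1: all luseogliflozin-treated patients with assayed Week 4 PK samples and no dosing or sampling deviation up to the 24-hour Week 4 sample that affects PK interpretation, regardless of completing the 12 weeks.

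Copying section 10.1 unchanged into section 9.3 is not quite enough. Section 4.3 says that only samples from luseogliflozin-treated patients will be assayed, which suggests that placebo patients may also be sampled. Read literally, section 10.1 would admit them without any concentrations.

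Settle the wording before unblinding. Under section 4.3 the concentrations are transferred only after database lock and code break, so membership rules fixed earlier cannot be influenced by them. The cost is one sentence, repeated in three places, and no new data.

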9.4. Pharmacodynamics

Considering the pharmacological effect of luseogliflozin, urinary glucose (quantitative) was selected to be measured in conjunction with the measurement of PK in the same subset of patients. The 24-hour pooled urine will be collected at Week 0 and Week 4 visits and the samples are to be sent to the central laboratory as detailed in the laboratory manual.

The results of urinary glucose are to be reported by the laboratory to the sponsor and Investigators only after locking of study data.

9.5. Dose proportionality, PopPK and PK/PD analysis

Dose proportionality will be assessed by plotting AUC_{0-t}/Dose versus Dose and Cmax/Dose versus Dose and additionally will be analysed by power model.

Population PK and PK/PD analyses may be performed using existing models previously developed for luseogliflozin. These analyses will be described in a separate Data Analysis Plan.

10. STATISTICS

10.1. Statistical analysis

This section briefly describes the planned statistical analysis. Details for the analysis will be provided in the separate statistical analysis plan (SAP) that should be finalized before the database lock.

Descriptive statistics:

- all quantitative data will be presented as number of valid observations, mean, 95%confidence interval (CI) for mean, standard deviation, median, min/max and 25th and 75th percentiles.
- all qualitative data will be presented as number of valid cases, number of cases for each response category, percentage of response category relative to the number of valid cases and exact Clopper-Pearson binomial confidence interval for proportion for each category.

Assessment of normality for the quantitative data will be performed using the Shapiro-Wilk test.

Disposition of study participants:

Disposition of study participants will be provided as follows:

- Number of screened patients (total)
- Screening failures (tabulated by reasons)
- Randomized patients by group
- Early terminated patients (tabulated by reasons)
- Study completers by group
- Allocation of patients to FAS and PPS populations

Baseline characteristics will be presented by group:

- Demographics (age, gender);
- Anthropometry (weight, height, BMI);
- Baseline laboratory data;
- Medical history and concomitant conditions;
- Prior and concomitant medications.

Efficacy analysis:

In order to meet the primary objective of the study, the efficacy of at least one dose of luseogliflozin as compared to placebo after 12 weeks of treatment in glycaemic control will be assessed from the change from baseline to W12 in HbA1c, in patients of the RS. Analysis of covariance (ANCOVA) will be used as the main method of assessment of the primary endpoint, with baseline (W0) HbA1c value being a covariate.

Unrestricted least significant differences (LSD) method will be applied to the ANCOVA results with the calculation of least-square (LS) means with 95% CI for LS means for the difference between each dose level and placebo.

Finally, to assess the dose-response of the investigation product with regards to the primary endpoint, contrasts will be build based on the ANCOVA results.

Before performing ANCOVA, a multiple imputation procedure will be used to impute:

- Missing data for the primary endpoint at 12 week (for patients with missing data at W8 and W12 and for patients with missing data at W12 only)
- Data collected after rescue therapy for non-controlled patients.

This approach allow to evaluate, as primary analysis, the hypothetical « proper effect » of luseogliflozin without additional effect of rescue therapy.

These analysis on primary endpoint will be done in the Randomised set (RS) and – additionally – in the per protocol set (PPS). Any differences between the results in RS and PPS will be investigated and explained, yet, RS will serve as the main analysis set at all times.

Two additional analysis will be performed on the primary endpoint on RS and PPS:

- Before performing ANCOVA, a multiple imputation procedure will be used to impute missing data for the primary endpoint at 12 weeks. Here data collected after rescue therapy will be taken into account in the analysis allowing to evaluate the effect of "treatment policy" of luseogliflozin + rescue medication VS placebo + rescue medication.
- Last observation carried forward (LOCF) method will be used to impute post rescue evaluations and other missing data at 12 weeks for the primary endpoint (for a bridging objective with studies performed on Japanese population)

The multiple imputation approach will be based on the regression method to impute values for each missing data at W008 and W012. Covariate use for the regression method will be auxiliary variables which might be predictive of both the chance of missing values and the underlying values themselves. Those additional auxiliary variables will be defined, before the blind is broken, in the SAP.

Secondary efficacy parameters – the following parameters will be assessed:

- 1) Quantitative parameters:
- Change in fasting plasma glucose,

- Change in postprandial plasma glucose,
- Change in body weight,
- Change in waist circumference

These parameters will be assessed and tested in the same spirit of the primary parameter and precision will be given in the SAP.

- 2) Qualitative parameters:
- The proportion of patients with HbA1c<7%
- The proportion of patients with HbA1c<6.5%

These parameters will be compared between the groups using the logistic model, including the fixed, categorical effect of treatment as well as the continuous, fixed covariates of baseline HbA1c.

Precision will be given in the SAP

Safety analysis will be performed by group for the following parameters:

- Frequency of emergent adverse events;
- Frequency of serious adverse events / ERIN;
- Frequency of adverse events related to the IMP (adverse drug reactions);
- Frequency of adverse events related to the conditions of the protocol;
- Frequency of any adverse events leading to treatment withdrawal;
- Frequency of all AE of Special Interest and frequency of each individual AEOSI;
- Laboratory parameters by visit;
- Frequency of laboratory parameter abnormalities by visit;
- Vital signs (HR, SBP, DBP) by visit;
- Frequency of vital signs (HR, SBP, DBP) abnormalities by visit;
- 12-lead ECG results by visit;
- Frequency of 12-lead ECG abnormalities by visit.

Frequency data will be compared between the groups using exact Fisher tests; numeric data will be compared between the groups using the t-test or Wilcoxon-Mann-Whitney test on ranks depending on the normality of the parameter distribution (which will be tested using Shapiro-Wilk test). Laboratory parameters, vital signs and 12-lead ECG data will be analysed using two-way ANOVA (or ANOVA on ranks, if the distribution is not meeting the normality criteria) to account for group and visit factors simultaneously.

Interim analysis

No interim analysis is planned for this study.

Study populations

- Randomized Set (RS):

All patients to whom a therapeutic unit was randomly assigned using IRS.

- Per Protocol Set (PPS):

All the patients of the RS that do not have any significant protocol deviations. List of deviations will be reviewed for the determination of their significance prior to the database lock and randomization list unblinding.

- Safety Set (SS):

All patients having taken at least one dose of study drug.

- **Pharmacokinetic set**: all patients for whom blood samples were collected with no deviations that might affect the pharmacokinetic interpretation

- **Pharmacokinetic/Pharmacodynamic set:** all included patients for whom blood samples and 24-hour urinary glucose measurements were collected with no deviations that might affect the PK and/or PD interpretations.

Significance level:

The type I error of the statistical tests will be set at 5% (two-sided situation).

Multiplicity issues:

In order to take into account the multiplicity of comparisons associated with the primary objective of the study (demonstration of superiority of at least one luseogliflozin dose as compared to placebo on the primary efficacy endpoint); a Bonferroni correction will be used for the primary analysis.

For secondary endpoints, the same strategy as the one use for primary analysis will be used for handling multiplicity issues for doses comparison and no adjustment to control the type I error for multiple endpoints will be used.

Statistical software

Statistical analysis will be performed using Microsoft R Open software, version 3.4.3 or higher (distributed by Microsoft R Application Network under the public license) or any similar software that will be finally determined at the stage of statistical analysis plan finalization.

Data coding

Medical history, concomitant conditions and adverse events will be coded using the MedDRA dictionary (the most up-to-date version by the time of database lock).

Prior and concomitant treatment will be coded using the ATC coding system.

